^{**} Additional pregnancy tests may be conducted during the participation of the trial if there is any suspicion of being pregnant

^{***} Type of Clinical assessment will be only completed if at a visit. If completed by phone no clinical assessment will take place

[~] May be taken at earlier timepoint if participant withdraws before day 120.

⁺ unblinded QST

[#] Study Completion

All follow up visits will be scheduled from baseline (Day 0). Each participant will complete treatment administration from day 0 to day 120 and will be followed up for 180 days in total. During this time, scheduled follow ups will be conducted via both telephone as well as clinic visits. No face to face study visits are planned after 120 days.

Following registration each participant will be given a diary that they will fill in and record their pain intensity in accordance with the schedule:

- Weekly between day 0 to day 90
- Daily Between day 90 to day 120
- Weekly between day 120 to day 180

Clinic Follow-Up Visits:

Participants will need to attend clinics for follow-up at 30, 60, 90 and 120 days. These visits should be arranged at the baseline visit post registration. The following data should be collected and assessments/activities performed at all visits (unless specified differently below):

- Concomitant medication
- AEs
- Further Provision of Anakinra
- Collection of safety blood samples
- Collection of research blood samples (30ml, day 120 only)
- · Clinical assessment and examinations including:
 - o Pain assessment on NRS from their pain diaries
 - o Limb Volume (days 60 and 120 only)
 - o Vital signs: BP, HR, and weight

Telephone follow ups:

Research nurses (RNs) will telephone participants approximately 2 weeks (+/-3 days) after each clinic visit up to day 120 when the last drug dose is administered, and a final telephone follow up at day 180 at the end of the trial. Telephone appointments will be arranged and conducted by local research teams. The following information should be collected and recorded on the appropriate CRF:

- Concomitant medication
- AEs
- Pain assessment up to 120 days at the end of drug administration (NRS)
- EQ5D-5L questionnaire at day 180

Efficacy Assessments

This trial is not designed to determine efficacy, however data will be collected on outcomes that will be used to determine efficacy in a future definitive trial. Outcomes are detailed in section 9.

Safety Assessments

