11 PROGRESSION CRITERIA

Monitoring for clinical trial progress will focus on recruitment and safety. This will be done by the IDSMC.

The following factors will be used to inform the decision to progress into the next stage of the trial:

- 1. **Recruitment**. Assessed 6 months from recruitment start. Initial recruitment rate of 0.5 participants each month per centre for the first 6 months from recruitment start.
- 2. **Safety**. Assessed 12 months from recruitment start (or later if it takes longer for 10 participants to be registered): For the first 10 registered participants, 3 or less reporting persistent pain (greater than 1 week) at injection site of at least moderate intensity (5 or greater on a 0-10 NRS scale) or substantial CRPS pain increase (>=2points NRS), ongoing for >1 month despite and from the time of pain-related treatment stop.
- 3. **Safety**. Assessed 12 months from recruitment start: Consider stopping if 30% or greater of study participants experiencing a serious adverse reaction (SAR).
- 4. **Recruitment and adherence**: At 12 months from recruitment start to have at least 12 participants registered and at least 50% of registered participants completing their active treatment.
- 5. **Futility**. After 12 participants have been recruited and completed 4 months treatment period, an average of no pain increase among completed participants (to visit 5/ 120 day) and at least one participant reporting at least 2 points of pain reduction on the NRS (rounded to the nearest whole number), both these criteria referring to the average pain recordings over the last two weeks before visit 5 / 120 day compared to baseline (0 day).

The IDSMC will use the above progression rules as a guide during regular monitoring with regards to trial progress and will provide a recommendation to the TSC concerning continuing the study. The above are not intended as strict stop/start criteria.

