14.2.1 Feasibility of Sample Size

Between the two recruiting sites we expect a recruitment rate of one patient every month (across the two centres) for the first 6 months from commencing recruitment. In the second 12 months recruitment rate will be expected to be two patients monthly across both sites.

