#### 25.1.2.3 Recruitment and adherence

Assessed 12 months after recruitment started the following will be reported:

- Number registered
- Number and proportion of those completing their treatment

To meet this criteria at least 12 paticipants should be registered and at least 50% of participants registered completing their active treatment.

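### The month-12 adherence criterion counts participants who cannot yet have finished 120 days of treatment, so at planned accrual its nominal 50% threshold needs about 9 of 10 possible completers

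*Protocol*

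**What the plan says.** Protocol section 11, item 4 sets the combined recruitment and adherence criterion: "At 12 months from recruitment start to have at least 12 participants registered and at least 50% of registered participants completing their active treatment". SAP 18.1.2 lists it in the same terms. SAP 25.1.2.3 gives the timing, "Assessed 12 months after recruitment started the following will be reported", then names the number registered and the number and proportion completing treatment, and closes: "To meet this criteria at least 12 paticipants should be registered and at least 50% of participants registered completing their active treatment". None of these places restricts the denominator to participants who have been in the trial long enough to finish, or says how someone still on treatment is counted.

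Two other statements fix the arithmetic. On treatment length, protocol 10.7 says: "Each participant will complete treatment administration from day 0 to day 120". On accrual, protocol 14.2.1 says "we expect a recruitment rate of one patient every month (across the two centres) for the first 6 months" and then "In the second 12 months recruitment rate will be expected to be two patients monthly across both sites".

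Section 11 ends by saying that the IDSMC uses these rules as a guide and that they are not meant as strict stop/start criteria.

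**The concern.** A participant registered in the last four months before the assessment cannot have completed 120 days of treatment, however well they adhere. Each such person adds one to the denominator and can add nothing to the numerator. The reported proportion therefore mixes adherence with the timing of registrations, and it falls when recruitment speeds up late in the year. That is an awkward property for a criterion meant to reward both recruitment and adherence.

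Other items in section 11 do wait for the data they need. The first safety item is deferred if 10 participants have not been registered by month 12, and the futility item waits until 12 participants have completed the 4-month treatment period. Item 4 has no such provision.

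At stake is the signal the IDSMC receives when it makes its recommendation to the TSC on continuing the study.

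**Working it through.** **Inputs**
- Assessment at 12 months; threshold 50% of all registered (protocol 11 item 4; SAP 25.1.2.3).
- Accrual 1 per month across both centres for 6 months, then 2 per month (protocol 14.2.1).
- Treatment 120 days (protocol 10.7); visit window plus or minus 3 days (protocol Table 4).
- Sample size 30 (protocol 14.2).
- True completion rate: not given in the documents. I assume 70%, 80% and 90%.

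**Reading the accrual plan.** The phrase about the second 12 months is loose. Read as months 7 to 18, it gives 6 × 1 + 12 × 2 = 30, exactly the stated sample size. Read as months 13 to 24, it leaves months 7 to 12 undefined. I use the first reading and test slower accrual below.

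**Ceiling at month 12**
- Treatment length: 120 / 30.44 = 3.94 months, so the last registration that can finish is at 12 − 3.94 = 8.06 months.
- Registered by month 12: 6 + 6 × 2 = 18.
- Registered by month 8.06: 6 + 2 × 2.06 = 10.1, so 10 people.
- Ceiling with perfect adherence: 10/18 = 55.6%.
- Needed for 50%: 9 of 18, hence 9 of the 10 who could have finished.

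**Chance of meeting the criterion.** With *m* participants able to finish, *k* completers needed and true completion *p*, the probability is P(Bin(*m*, *p*) ≥ *k*). For the main case at 70%: 10 × 0.7⁹ × 0.3 + 0.7¹⁰ = 0.121 + 0.028 = 0.149.

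| Scenario at month 12 | Ceiling | Needed | 70% | 80% | 90% |
|---|---|---|---|---|---|
| Planned accrual, main case | 10/18 = 56% | 9 of 10 | 15% | 38% | 74% |
| Registrations at the start of each interval | 11/18 = 61% | 9 of 11 | 31% | 62% | 91% |
| Registrations at the end of each interval, day-120 visit 3 days late | 9/18 = 50% | 9 of 9 | 4% | 13% | 39% |
| Accrual stays at 1 per month (12 registered) | 8/12 = 67% | 6 of 8 | 55% | 80% | 96% |

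In the third row, 123 / 30.44 = 4.04 months moves the cut-off to month 7.96, just before a registration at month 8.0. The probabilities are *p*⁹.

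**Expected proportion, main case:** 10 × *p* / 18 = 38.9%, 44.4% and 50.0% at 70%, 80% and 90% completion.

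**Direction with faster accrual.** At 3 per month after month 6, registered = 6 + 18 = 24 and able to finish = 6 + 3 × 2.06 = 12.2, a ceiling of about 51%. Better late recruitment makes the criterion harder to meet.

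**The case against.** The strongest reply is that little hangs on this figure. Section 11 makes the criteria a guide. The examples of reasons for termination in protocol 10.10 include insufficient registration but not low completion. The IDSMC has an independent biostatistician (protocol 4.8). SAP 25.1.1 also gives the committee the numbers lost to follow-up, still in follow-up and finished, with treatment compliance split at days 30, 60, 90 and 120. A careful committee could see that the shortfall is immaturity of the data. All of this stands, and it limits the severity. It does not repair the rule, which, applied as written, still returns 'not met'.

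A second reply is that completing could include people still on course. That reading would remove the ceiling. Neither document states it, and the SAP's planned report of the number and proportion completing treatment points to people who have finished. If the wider reading is meant, it needs to be written down, because the two readings can give opposite answers.

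A third is that the 56% rests on one reading of a loosely worded accrual sentence and on small whole-person counts. That is fair, and the table shows the range. The ceiling moves between 50% and 67%, but it is present in every scenario examined.

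A reader might also infer that the criterion fails whenever adherence is good, or that it measures accrual timing alone. The figures do not support either. At planned accrual, 90% completion meets it 74% of the time in the main case, and the probability rises from 15% to 74% with completion alone. The criterion responds to adherence, but against a much higher bar than the stated one.

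**Conclusion.** The point holds in limited form. At planned accrual, the nominal 50% threshold acts as a requirement of about 90% among those who could have finished. The ceiling is about 56%, ranging from 50% to 61% with the timing of registrations and the visit window, and 67% if accrual stays at 1 per month. With true completion of 80%, the criterion would be missed about 62% of the time (1 − 0.38) at planned accrual and about 20% of the time with 12 registered.

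These results assume the months 7 to 18 reading of the accrual plan, the assumed completion rates, and independence between participants.

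It would be tempting to conclude that the trial could be stopped because of this rule. The documents do not support that: the criteria are non-binding, and the consequence is a misleading signal to the IDSMC. No primary or secondary outcome analysis uses this proportion. I rate it as something that should be fixed, below the level of a must-fix.

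**What to change.** In protocol section 11 item 4, and in SAP 18.1.2 and 25.1.2.3:
- compute the 50% among participants registered at least 120 days, plus the 3-day window, before the assessment date;
- keep the requirement of at least 12 registered on all registered participants;
- report those still on treatment as a separate count.

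With 10 participants in the restricted denominator, 5 completers are needed, and the criterion is met with probability 95%, 99% and over 99.9% at 70%, 80% and 90% completion. If the 3-day allowance leaves 9, then 5 of 9 are needed and the figures are 90%, 98% and 99.9%.

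The cost is a short wording change in each of the three places and a proportion that rests on about 9 to 10 people. Little is lost by that, since only those participants can yet show whether treatment is completed. The documents do not show whether the month-12 assessment has already been made. If it has, the report should state which denominator was used and give the restricted proportion beside it.

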12 SUB-STUDIES

QST in this clinical trial is part of a standard of care when assessing patients with CRPS. One risk of performing the mechanical component of QST is the patients can observe the testing process and this visual aspect may bias the sensory profile results. The aim of this sub-study is to determine whether participant observation of the assessment leads to visual bias and alters the results of QST.

We will do this by performing the test at day 0 (Baseline) blindfolded to mask visual cues and non-blindfolded which is standard. Therefore, the QST will be performed twice on each participant at baseline with the order determined at random via a web-based randomisation system.

The aim is to compare the QST results (measured as a standardised z-score) between mechanical components measured with and without visual cues. The QST measurements will be explained and demonstrated by a trained member of the research team prior to measurement. The methodology of performing the QST is detailed in 22.3. Once the QST process has been explained, the measurement will be performed both blindfolded and non-blindfolded in an order determined at random.

The impact on the main study will be negligible as this is not an interventional measure and pain measures are unaffected by QST. A statistical plan will be detailed separately from the statistical analysis plan for the main study.

Both the Liverpool and London sites will take part in this sub-study.

13 SAFETY REPORTING

Safety reporting in clinical trials is a legal and ethical requirement and it is imperative that all applicable requirements detailed here are followed during the trial.

13.1 Terms and Definitions

Adverse Event (AE)

Any untoward medical occurrence in a patient or clinical trial subject administered a medicinal product and which does not necessarily have a causal relationship with this treatment.

An AE can therefore be any unfavourable and unintended sign (including an abnormal laboratory finding, for example), symptom or disease temporally associated with the use of a medicinal product, whether or not considered related to the medicinal product.

Adverse Reaction (AR)

Any untoward and unintended response to an IMP related to any dose administered.

Condition Specific Adverse Event

Persistent pain at injection site (greater than 1 week) of at least moderate intensity (5 or greater on a 0-10 NRS scale) and increase in CRPS associated pain(>=2points NRS), ongoing for >1 month.

Serious Adverse Event (SAE)

Any untoward medical occurrence or effect that at any dose results in death, is life-threatening, requires hospitalisation or prolongation of existing hospitalisation, results in persistent or significant disability or incapacity, or is a congenital anomaly or birth defect.

Serious Adverse Reaction (SAR)

An AR which meets the definition of serious (see Section 13.2) is a SAR. A SAR event that has been assessed as 'expected' (see Section 13.5 Expectedness) according to the Reference Safety Information (RSI) (see below) will remain classified as a SAR only, however some SARs that are considered 'unexpected' will be further classified as a Suspected Unexpected Serious Adverse Reaction (SUSAR) (see below).

Suspected Unexpected Serious Adverse Reaction (SUSAR)

An AR that is classed in nature as serious and "unexpected" (i.e. not listed within the RSI approved for the trial by the MHRA and current at the time of onset of the SUSAR).

Reference Safety Information (RSI)

The information used for assessing whether an AR is expected (see section 13.5). This is contained in the SmPC for the product and must be approved for use by the MHRA. The RSI used to assess the expectedness of a SAR must be the current approved version at the time of onset of the SAR. The RSI for this trial is defined in section 13.5.1.

13.2 Assessment of Seriousness

The assessment of seriousness of safety events should be performed by an appropriately delegated, medically qualified member of the site research team.

An adverse event / reaction is assessed as serious if it:

Results in death;

- Is life threatening (i.e. the investigator considers the event places the subject at immediate risk of death from the experience as it occurred (this does not include an adverse experience that, had it occurred in a more severe form, might have caused death));
- Requires hospitalisation or prolongation of existing hospitalisation (hospitalisation is defined as an
 inpatient admission, regardless of length of stay, even if the hospitalisation is a precautionary
 measure for continued observation. Hospitalisations for a pre-existing condition, including elective
 procedures that have not worsened, do not constitute an SAE);
- Results in persistent or significant disability or incapacity (substantial disruption of one's ability to conduct normal life functions);
- Consists of a congenital anomaly or birth defect (in offspring of subjects, or their partners, taking the IMP regardless of time of diagnosis);
- Other important medical events (these may not result in death, be life-threatening, an overdose, a
 secondary malignancy or require hospitalisation, but may be considered an SAE/experience when,
 based upon appropriate medical judgment, they may jeopardise the subject and may require
 medical or surgical intervention to prevent one of the outcomes listed in this definition).

13.3 Severity of Adverse Events

All AEs should be assessed for severity. The assignment of the severity/grading should be made by the investigator responsible for the care of the participant using the definitions in the table below:

Table 4: Severity Grading

Severity	Description
Mild	Does not interfere with routine activities.
Moderate	Interferes with routine activities.
Severe	Impossible to perform routine activities.
Life-Threatening	
Death	

N.B. A distinction is drawn between **serious** and **severe** AEs. Severity is a measure of intensity (see above) whereas seriousness is defined using the criteria in Section 13.2. Hence, a severe safety event need not necessarily be a "serious" safety event.

13.4 Assessment of "Causality" - Relationship to Trial Treatment/Intervention

The assignment of the causality should be made using the definitions in the table below:

Table 5: Definitions of Causality

Relationship	Description
Unrelated	There is no evidence of any causal relationship.
	N.B. An alternative cause for the AE should be given
Unlikely	There is little evidence to suggest there is a causal relationship (e.g. the event
	did not occur within a reasonable time after administration of the trial
	medication). There is another reasonable explanation for the event (e.g. the
	participant's clinical condition, other concomitant treatment).
Possibly	There is some evidence to suggest a causal relationship (e.g. because the
	event occurs within a reasonable time after administration of the trial
	medication). However, the influence of other factors may have contributed to
	the event (e.g. the participant's clinical condition, other concomitant treatments).

Probably	There is evidence to suggest a causal relationship and the influence of other factors is unlikely.
Almost certainly	There is clear evidence to suggest a causal relationship and other possible
	contributing factors can be ruled out.

Events that are assessed as being possibly, probably or almost certainly related will be reported as having a reasonable possibility of being related, and events assessed as unrelated or unlikely will be reported as having no reasonable possibility of being related.

Assessment of causality should be made based on known safety profiles of IMP, or SmPC, or Investigator's Brochure (IB) and known risk profiles of other drugs in the same class. If any doubt about the causality exists the local investigator should inform the LCTC who will notify the CI. In the case of discrepant views on causality between the treating investigator and others, the opinion of the treating investigator will never be downgraded and the MHRA/REC will be informed of both points of view.

13.5 Assessment of "Expectedness"

The CI (or delegate) for the INCA trial is responsible for determining whether a safety event is expected or unexpected, however a Medical Reviewer will not assess their own patients, these patients will be assessed by an independent Medical Reviewer. There is no requirement for a reporting investigator to make an assessment of expectedness.

An event will be considered unexpected if it is not listed within the current and approved RSI (see section 13.5.1) for the study at the time of the event's onset. The nature, severity, or frequency of the event should be considered – if this is not consistent with that described for the type of event in the RSI the event should be assessed as unexpected.

13.5.1 Reference Safety Information / Information used to Assess Expectedness

The RSI for INCA is Kineret subcutaneous injection 100mg, derived from section 4.8 of the SmPC, available at https://www.medicines.org.uk/emc/product/559

13.6 Time Period for Active Monitoring of Safety Events

IMPORTANT: Any safety events occurring after the end of the below-described "active monitoring" period which meet the definition of serious (see section 13.2) and are recorded for this study (see section 13.1) must continue to be reported by sites to the LCTC in accordance with the timeframes and procedures described in section 13.12. The same processes established for SAEs within the active monitoring period should be followed for these events.

Active monitoring of safety events experienced by trial patients will be carried out from the time of trial consent. Between the point of consent and baseline (Day 0) only safety events which are related to trial procedures will be monitored. Thereafter all safety events will be monitored, beginning with the baseline visit (0 Day), then every 30 days at clinic visits, and at all telephone calls between clinic visits until the 120 day visit (end of treatment). Further safety events will be monitored at the end of the study on day 180 which is 60 days after the last dose of Anakinra.

Pregnant women will be followed up until a completed outcome of pregnancy (see Section 13.8 for more information on reporting pregnancy).

13.7 Notes on Safety Event Recording

The following events must be recorded for the purposes of the trial:

- An exacerbation of a pre-existing illness
- An increase in frequency or intensity of a pre-existing episodic event/condition

- A condition (even though it may have been present prior to the start of the trial) detected after trial drug administration
- Continuous persistent disease or symptoms present at baseline (0 day) that worsens following the administration of the study/trial treatment
- Laboratory abnormalities that require clinical intervention or further investigation (unless they are associated with an already reported clinical event).
- Abnormalities in physiological testing or physical examination that require further investigation or clinical intervention
- Injury or accidents
- Pregnancy (See section 13.8 for more details)
- Weight loss of ≥4% within 4 months

Do not record:

- Medical or surgical procedures the condition which leads to the procedure is the AE
- Pre-existing disease or conditions present before treatment that do not worsen
- Situations where an untoward medical occurrence has occurred e.g. cosmetic elective surgery¹
- Overdose of medication without signs or symptoms*2
- The disease being treated or associated symptoms/signs unless more severe than expected for the participant's condition

*N.B. If overdose occurred **with** resulting signs and symptoms that meet the protocol criteria for AE/AR/SAE/SAR/SUSAR then they should be reported accordingly (see section 13.12 for more information) and the overdose highlighted to the LCTC team.

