10.7 Schedule for Assessments and Follow-up

All assessments and follow up are to be conducted in line with the Schedule of Assessments below: *Table 4: Schedule of Assessments:*

				Visit 1	Telephone follow up 1	Visit 2	Telephone follow up 2	Visit 3	Telephone follow up 3	Visit 4	Telephone follow up 4	Visit 5	Telephone follow up 5	
		Screening	Pre-baseline Telephone visit	Baseline^	Baseline +2wks	Day 30*	Day 30 +2wks	Day 60*	Day 60 +2wks	Day 90*	Day 90 +2wks	Time Point Day 120*	Day 180#	Premature Discontinuation
Proced	ures													
Signed Form	Consent	Х												
Registr	ation			Х										
Assess Eligibili	ment of ty Criteria	Х		Χ										
History	of Medical (including raphics)	Χ												
Review Concor Medica	mitant	Χ		Х	X	X	Х	Х	Х	Х	Х	Х	Х	х
(Daily a	ntervention after e to day			Х		Х		Х		Х		Х		
	Medical History and examinati on	Х										Х		X***
Clinical Assessment	CRPS History and Limb Examinat ion	Х										Х		X***
Clinical	Vital signs, weight, height, HR and BP	Х		Х		Х		X		Х		Х		X***
	Limb Volume	Х						Х				Х		
applica	or Blood	Х				Х		Х		х		х		
(CXR)	Radiograph and TB testing†	Х												

				Visit 1	Telephone follow up 1	Visit 2	Telephone follow up 2	Visit 3	Telephone follow up 3	Visit 4	Telephone follow up 4	Visit 5	Telephone follow up 5	
		Screening	Pre-baseline Telephone visit	Baseline^	Baseline +2wks	Day 30*	Day 30 +2wks	Day 60*	Day 60 +2wks	Day 90*	Day 90 +2wks	Time Point Day 120*	Day 180#	Premature Discontinuation
TB scre	ening skin test†	Х												
Issue and coll	pain diary lection	Х		Х		Х		Х		Х		Х		
Numerio Score Pain	cal rating for CRPS	Х	Х	X	×	X	X	X	X	X	X	Х	Х	Х
CRPS score	Severity			Х		Х		Х		Х		Х		
EQ5D-5	5L			X		Х		Χ		Х		Х	X	
PHQ-9				Х		X		Χ		Χ		Х		
HADS				X		X		Χ		X		X		
BPI				X		X		Х		Х		X		
Work S	tatus			Х								Х		
QST-bli unblinde				Х								X+		
Global of Chan	Impression ige											Х		
Assessi Adverse	ment of Events			Х	Х	Х	X	Х	Х	Х	Х	Х	Х	Х
Blood sample collection	Clinical Chemistr y/ Hepatic Function	X				Х		X		X		X		X
Blo	Haematol ogy	Х				Х		Х		Х		Х		х
Serology	HIV/Hep atitis B and C‡	х												
Researd	ch Blood	X			/ 6							X~		

Each Time point for follow up schedule can be +/- 3 days.

†unless a TB screen of either method listed has been done in the 3 months prior to the screening visit ‡unless a screen has been done in the 3 months prior to the screening visit

[^]Time between Screening and Baseline should be no more than 14 days.

^{*} Face to face appointment

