#### 23 Baseline Characteristics

Descriptive statistics will be reported overall. Categorical data will be summarised by frequency and percentages with the denominator as the number registered. Continuous data will be summarised by mean, standard deviation (SD), median, inter-quartile range (IQR), minimum and maximum.

Patient demographics are to be summarised as follows from Form 1:Screening:

- Age (years)
- Age categorised for EudraCT
  - Adults (18-64 years)
  - o From 65 to 84 years
  - o 85 years and over
- Sex
- o Male
- o Female
- Ethnicity
  - Arab
  - Asian Other
  - Bangladeshi
  - Black African
  - o Black Caribbean
  - Black Other
  - Chinese
  - Gypsey or Irish Traveller
  - Indian
  - o Irish
  - Other ethnic group

- Other mixed
- Other white
- Pakistani
- White and Asian
- White and Black African
- o White and Black Caribbean
- o White British
- Clinical chemistry/Hepatic functions tests\*
  - o Sodium
  - Potassium
  - o Urea
  - Creatinine
  - Biblirubin
  - o ALT
  - Alkaline Phosphatase
  - GGT
- Haematology Tests\*
  - o Full Blood count
  - o Full Blood count differential
  - Neutrophil count
  - Neutrophil count result (10^9/L)

\*All Clinical chemistry/Hepatic functions tests and Haematology Tests will be summarised with the categories Normal, Abnormal NCS and Abnormal CS as collected on the CRF (bar the Neutrophil count result which is numeric).

The below patient demographics are collected on both Form 1 Screening and Form 2 Baseline, summaries should be provided for Form 2 but if missing the value on Form 1 should be used:

Vital signs

- Height [cm]
- Weight [kg]
- Heart rate [bpm]
- Blood pressure [mmHg]

Limb volume

• Limb volume (Lower) [cm]

LCTC\_ST003\_TEMP1: SAP Template, V0.1, 08/01/2021 (developed using LCTC\_GE001\_TEMP4: LCTC Template of a Template, V1.0, 04/09/2020)

CLINICAL TRIALS CENTRE LCTC

Limb volume (upper) [cm]

Average pain score over last 24 hours:

At baseline

Research blood samples:

Consent to blood samples (Yes/No)

Blood sample taken (Yes/No)

**24** Compliance with Interventions

Exposure to treatment will be assessed by mean dose (mg) per participant. Dosing is once daily for a

maximum of 120 days; the mean and median number of doses per participant over the treatment

period (expressed as number of days treatment administered for) will be summarised.

Compliance of treatment will be captured by summarising the number of returned used syringes

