25.2.3.2.11 Work status

25.2.3.2.11.1 Derivation

Work status is recorded at baseline and day 120, with the following categories:

Employed

Self-employed

Not working.

25.2.3.2.11.2 Analysis

Categorical data will be summarised using frequencies and percentages at baseline and day 120 with

the denominator being those who completed the question at each timepoint.

To compare work status at baseline and day 120 a cross-tabulation will be provided with two

percentages using the denominators of total number of patients in the work status category at

baseline and at day 120 i.e. row and column percentages. A simiplified table of working (classified as

employed or self-employed) and not working at baseline and day 120 will also be provided.

26 Safety Evaluations

All non-serious adverse events (AEs) and SAEs reported by the clinical investigator will be presented

in a table (or non-serious adverse reactions (ARs) and SARs if the study does not capture unrelated

AEs). The number (and percentage) of patients experiencing each AE/SAE will be categorised by

severity (mild, moderate, severe). For each patient, only the maximum severity experienced of each

type of AE will be displayed. The number (and percentage) of occurrences of each AE/SAE will be

presented. No formal statistical testing will be undertaken.

27 Additional Analyses

No additional analysis planned.

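### The SAP has no check of follow-up weights against the protocol's recordable weight-loss event, so a case that a site does not calculate would not be found by any planned analysis

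*Protocol*

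**What the plan says.** Protocol 13.7 opens its list with "The following events must be recorded for the purposes of the trial". The last of its nine items is "Weight loss of ≥4% within 4 months", the only one with a numeric threshold. The section names no reference weight and does not say whether the window runs from a fixed date or rolls.

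The Schedule of Assessments (Protocol 10.7, Table 4) has a row "Vital signs, weight, height, HR and BP", marked at screening, baseline and days 30, 60, 90 and 120, and at premature discontinuation only if that takes place at a visit. The text on clinic follow-up visits repeats "Vital signs: BP, HR, and weight". The last scheduled weight is at day 120: "No face to face study visits are planned after 120 days".

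SAP 23 uses weight as a baseline characteristic: "summaries should be provided for Form 2 but if missing the value on Form 1 should be used". The SAP's only other mention of body weight is the dosing description in SAP 14. On safety, SAP 26 says "All non-serious adverse events (AEs) and SAEs reported by the clinical investigator will be presented", and SAP 27 says "No additional analysis planned".

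**The concern.** The event is a calculation on two measured numbers, yet the analysis plan takes it only from what a site chooses to write on an AE form. To report it, staff must compare the current weight with one taken weeks or months earlier and compute a percentage. A loss that builds up over several visits is easy to overlook, whereas the analyst will hold whatever weights were taken.

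Safety and tolerability is the primary objective. A reader of the final report could take the AE count for this item as its frequency, although the analysis plan has no means of showing whether that count is full.

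**Working it through.** The documents give no figure to reproduce here. The check sets the sections side by side; the arithmetic only gives scale.

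**1. Is the event mandatory?** Yes (Protocol 13.7). It is not a condition-specific AE (Protocol 13.1, SAP 25.2.2.1), so it enters the primary outcome only if it is serious.

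**2. Are the data scheduled?** Yes, at baseline and four later visits across the 120-day treatment period. They are scheduled, not guaranteed: a missed visit, a discontinuation handled by telephone, or withdrawal from follow-up leaves gaps.

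**3. Does the SAP compare follow-up weight with an earlier weight?** No. SAP 23 stops at baseline, SAP 26 uses investigator reports, and SAP 27 adds nothing.

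**4. Does the SAP treat any other event differently?** Yes. For the pain events in the progression criteria, SAP 25.1.2.2 uses both the site's yes/no answer at each visit and a derivation from the data, with the stated aim of missing none. Weight loss has no such pairing.

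**5. How large is a 4% loss?** 0.04 × body weight: 2.0 kg at 50 kg, 2.8 kg at 70 kg, 3.2 kg at 80 kg, 4.0 kg at 100 kg.

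**6. What does one missed case do?** With the planned 30 participants, 1/30 = 3.3 percentage points.

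**7. Illustration under assumptions.** The documents give neither the incidence p nor the share s of cases that sites detect. With n = 30, expected missed cases = 30 × p × (1 − s), and the chance of at least one missed case = 1 − [1 − p(1 − s)]^30.

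| Assumed p | Expected cases | Missed, s = 95% | Missed, s = 80% | Missed, s = 50% |
|---|---|---|---|---|
| 5% | 1.5 | 0.075 (7%) | 0.3 (26%) | 0.75 (53%) |
| 10% | 3.0 | 0.15 (14%) | 0.6 (45%) | 1.5 (79%) |
| 20% | 6.0 | 0.3 (26%) | 1.2 (71%) | 3.0 (96%) |

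Brackets show the chance of at least one missed case. The spread from 7% to 96% shows how little can be said about size.

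**8. Does the undefined reference matter?** Yes. Take a participant at 70 kg at baseline who rises to 70/0.96 = 72.92 kg and returns to 70 kg by day 120. Against baseline the loss is 0%; on a rolling reading it is (72.92 − 70)/72.92 = 4.0%, an event. If screening is the reference, baseline follows 7 to 14 days later (Protocol 10.5 and Table 4), so day 120 falls 127 to 134 days after it, and whether that lies inside the window needs a rule.

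**The case against.** The strongest reply is that nothing required is missing. Sites must record the event, all safety events go on an AE form sent to the trials unit within seven days (Protocol 13.12), AEs are assessed at the same visits at which weight is taken, and SAP 26 tabulates whatever is reported. The protocol promises no analysis of weight. Follow-up blood pressure and heart rate have no derived summary either, and the pain events receive double capture because they belong to the primary outcome and the progression criteria. All of this stands, and it makes the point an improvement, not a breach of the plan.

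A reader might infer that missed cases will certainly go unreported, or that nothing in the trial compares weights over time. The documents do not support that. Protocol 15.3 provides central checks of each participant's data over time, with queries back to sites. The follow-up CRF, the monitoring plan, the data management plan and the programmed data checks are not available here and may cover this event. The versions that the SAP cites for the monitoring plan (16/05/2022) and the data management plan (14/04/2022) predate protocol version 4.0 (08/11/2022), whose amendment log lists this event as an addition; later versions may exist.

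A reader might also suppose that a derived count would be the true frequency. It would not: weights will be missing, perhaps most often in participants who stop early, and an AE report may be the only record for them.

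**Conclusion.** The point holds as a gap in the SAP: a case of weight loss at the protocol's threshold that a site does not calculate would not be picked up by any analysis in the SAP. Whether it would be caught elsewhere in the trial cannot be told from the documents.

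The size is small and unknown. Each missed case is worth 3.3 points if 30 participants are treated; the probabilities above rest entirely on assumed incidence and detection. It would be wrong to conclude that the primary outcome is biased, since it changes only if such an event is also serious. This is a worthwhile low-cost addition and not a fault that threatens the trial's conclusions.

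**What to change.** 1. The sponsor states, for Protocol 13.7, which weight is the reference and how the four-month window is read (from a fixed date or rolling, and how visit windows of ±3 days are treated). This review does not choose between them.
2. SAP 26 adds, in the safety set, a derived flag: percentage change = 100 × (weight at visit − reference weight)/reference weight, flagged if −4% or lower on the stated definition, at any available weight up to day 120.
3. Before data freeze, query every flagged case that has no matching AE record.
4. Report the number and proportion of participants with the event by site report, by derivation and by either, with the number who have at least one follow-up weight. Say that the derived count supplements AE reporting and does not replace it.
5. Reconcile the name of the baseline form: SAP 23 takes baseline weight from Form 2, while SAP 25.1.2.4, Table 25-1 and 25.2.3.2.1.1 call the baseline form Form 4.

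The cost is one derived variable, one table and a few data queries, using measurements already scheduled. The threshold in the protocol stays as it is, and no visit, dose or clinical rule changes.
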